### **3.3. Withdrawals**

Subjects who become noncompliant will still be followed for outcomes. Noncompliant will be defined as missing one or more study visits. Additionally, if enrolled in Intervention B, noncompliant will be defined as missing six or more group sessions. Subjects who withdraw from the study after randomization will be excluded from further follow-up. Outcomes ascertained up until the time of withdrawal will be reported in an intent to treat fashion. Those who withdraw prior to determining the primary outcome will be accounted for by randomizing an equal number of additional subjects.

### **3.4 Outcomes**

#### **Primary outcome:**

Our primary outcome will be insulin sensitivity/resistance.

#### **Secondary outcomes:**

- Maternal weight gain: change from baseline body weight at 3 months and at 6 months
- Development of diabetes postpartum (based on a fasting plasma glucose test >99mg/dL or the 75-g, 2-hour OGTT > 199mg/dL)
  - Initiation (if newly diagnosed postpartum) or continuation/restarting (if had gestational diabetes and now diagnosed as diabetes mellitus) of insulin and/or oral medications
- Worsening blood pressure in the postpartum period
  - Blood pressure:  $\geq 140/90$  mm Hg or use of anti-hypertensive medication or increased dose of anti-hypertensive medication
- Other metabolic issues (e.g., thyroid disease, fatty liver disease etc.) discovered through chart review)

The primary outcome (insulin sensitivity/resistance) will be evaluated via the HOMA insulin sensitivity or resistance tests.

Secondary outcomes will be reviewed as follows:

1. Maternal weight gain: Change from baseline body weight at enrollment of study as compared to body weight at 3 month postpartum study visit and 6 month postpartum study visit.
2. Development of diabetes postpartum: As part of routine postpartum care, women at risk for development of diabetes postpartum are evaluated with a fasting plasma glucose test or 2 hour oral glucose tolerance tests. These tests are part of routine clinical care (when indicated) and will be accessed by the research staff through chart review.
3. Worsening blood pressure in the postpartum period: Blood pressure recorded at the time of enrollment to the blood pressure recorded at the 3 month postpartum study visit and 6 month postpartum study visit will be compared. The addition of an anti-hypertensive medication or increased dose of an anti-hypertensive medication will be accessed by the research staff through chart review.
4. Other metabolic issues, such as thyroid disease, fatty liver disease, etc: Additional metabolic issues will be reviewed by the research staff through chart review.

The PI will review and validate the diagnosis for all subjects identified to have the primary outcomes. These reviews will be conducted masked to treatment group. If there is uncertainty, a co-investigator will review the chart and discuss with the co-investigators as needed and make a final determination regarding the outcome.

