Additionally, subjects enrolled in Intervention B will have 12 weekly group sessions with an X-PERT trained professional. The group sessions will last approximately 1.5 hours and have no more than 20 subjects enrolled in each group. Subjects will be welcome to bring their infant to each group session. A babysitter will not be provided

so the subject will be responsible for taking care of her own infant. Breastfeeding or formula feeding during the group session will be encouraged. The group session is available to research study participants only; besides the infant, no additional family members will be allowed. If enrolled in Intervention B, subjects will have up to 15 in person visits.

Blood and urine samples will be collected at each study visit. The first study visit will occur at 2-3 weeks postpartum. The second study visit will occur at 3 months postpartum (+ 3-week window). The third study visit will occur at 6 months postpartum (+ 3-week window). All samples will be collected while the patient is fasting (not eating for at least 8 hours). A standard 4oz sterile urine collection cup will be provided for each urine sample. Urine will be checked for glucose and ketones by dipstick. Approximately 20mL of blood will be collected with each sample. The blood samples will be used for the following tests:

- Hemoglobin A1c (HgA1c)
- Lipid panel
- Homeostatic Model Assessment (HOMA) test for insulin sensitivity or resistance: we will measure fasting insulin and glucose levels. Fasting will be defined as the last meal more than 8 hours before testing (i.e. overnight fasting). We will be using the following computation to calculate HOMA.

$\text{HOMA-IR} = \frac{\text{Glucose} \times \text{Insulin}}{22.5}$	$\text{HOMA-IR} = \frac{\text{Glucose} \times \text{Insulin}}{405}$
$\text{HOMA-}\beta = \frac{20 \times \text{Insulin}}{\text{Glucose} - 3.5} \%$	$\text{HOMA-}\beta = \frac{360 \times \text{Insulin}}{\text{Glucose} - 63} \%$
Glucose in Molar Units mmol/L	Glucose in mass units mg/dL

Blood and urine samples will be taken to the lab to complete the above-mentioned tests and/or stored at -80°C in our perinatal research department for later processing. The blood and urine will be stored in the perinatal research department with the potential for future metabolic testing that relates to this research study. Only the PI and research staff involved with this study will have access to the stored samples.

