### **Visit #1 at 2-3 weeks postpartum, Visit #2 at 3 months postpartum and Visit #3 at 6 months postpartum.**

All patients will have a blood sample and urine sample collected at each study visit. The blood and urine sample will be collected while the patient is fasting. The fasting period is defined as at least 8 hours without food. The subjects will be allowed to drink water. All subjects will have the option of first morning visits in order to utilize the overnight period as the fasting period.

A standard 4oz sterile urine collection cup will be provided for each urine sample. Urine will be checked for glucose and ketones by dipstick. Approximately 20mL of blood will be collected at each study visit. The urine sample will be assessed for urine glucose and ketones by urine dipstick. The blood samples will be used for the following tests: Hemoglobin A1c (HgA1c), lipid panel, homeostatic Model Assessment (HOMA) test for insulin sensitivity or resistance. The samples will be taken to the lab and/or stored at -80°C in our perinatal research department for later processing for use in the research study.

Subjects' vital signs, including blood pressure, waist circumference, height and weight, will also be recorded.

The data collected will not be used for clinical diagnosis or treatment purposes. Subjects will be reassured that participation in the study is voluntary and will not interfere with diagnosis or treatment of her condition.

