#### **5. Criteria for exclusion of subjects:**

- Enrolled in another trial that may affect outcome
- Subject who is unlikely to be followed-up after delivery

- Diabetes mellitus on medication; gestational diabetes requiring medication at the recruitment visit
- Other serious medical condition at the discretion of the PI (e.g., heart failure, kidney failure, severe asthma)
- Planned pregnancy during study period

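### The 'development of diabetes' outcome has no baseline condition and depends on which routine test was ordered, so glucose already raised at entry can be counted as new diabetes.

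*Combined protocol and SAP*

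**What the plan says.** Section 3.4 names the outcome "Development of diabetes postpartum" and defines it as "based on a fasting plasma glucose test >99mg/dL or the 75-g, 2-hour OGTT > 199mg/dL". The two limbs are joined by 'or'. No source, repeat test or baseline value is given for either.

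The sub-item on starting or resuming glucose-lowering medication uses different language. It refers to women "if had gestational diabetes and now diagnosed as diabetes mellitus".

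On ascertainment, Section 3.4 says that "women at risk for development of diabetes postpartum are evaluated with a fasting plasma glucose test or 2 hour oral glucose tolerance tests", and adds: "These tests are part of routine clinical care (when indicated) and will be accessed by the research staff through chart review".

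Section 5 has one glycaemic exclusion: "Diabetes mellitus on medication; gestational diabetes requiring medication at the recruitment visit". It sets no glucose limit.

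Separately, for HOMA, Section 3 says "we will measure fasting insulin and glucose levels", in fasting samples from all women at all three visits. Section 3.1 says of the visit data: "The data collected will not be used for clinical diagnosis or treatment purposes".

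**The concern.** The outcome's name promises new disease, but nothing in the plan requires a woman to be free of the condition at the start. In the same section, weight change and worsening blood pressure are both compared with the value at enrollment. Diabetes has no such comparison.

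A second problem is that the outcome is seen only where a provider ordered a test, and the provider's choice decides which limb applies. Section 2 describes the trial as non-blinded, and the masked review in Section 3.4 is written for the primary outcome only.

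At stake is what a reader may conclude from the diabetes result. A rate could be read as incidence when part of it was present at entry, and a difference between arms could reflect testing rather than disease.

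**Working it through.** **The plan's own figures.** No event rate, power or sample size is stated for this outcome. The sample size in Section 12 rests on HOMA-IR alone. With means 1.4, 1.05 and 1.05, the grand mean is 1.1667 and the squared deviations sum to 0.0817. With variance 0.8 and 96 per group, the noncentrality is 96 × 0.0817 / 0.8 = 9.8, and the F-test on 2 and 285 degrees of freedom has power 0.803. The stated 80% reproduces and does not involve the diabetes outcome.

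**Who can be counted, from the text.**

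1. A single fasting value of 100 mg/dL satisfies the first limb, so it is an event.
2. Women with unmedicated diabetes, diet-managed gestational diabetes, or untreated fasting glucose above 99 mg/dL pass the Section 5 exclusion.
3. No section removes such women from the outcome or compares them with an entry value.
4. So a woman in step 2 who has a routine test showing the same state is recorded as having developed diabetes.

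**Possible size of the carry-over (assumption, not from the documents).** Suppose study-visit fasting glucose were used in all women, with the same normal distribution at visit 1 and 6 months, SD 10 mg/dL and correlation r between visits. Readings are whole numbers, so above 99 is taken as above 99.5. The share already above the cut-off is P(both visits > 99.5) / P(6 months > 99.5).

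| Mean | r | P(6 months > 99.5) | P(both > 99.5) | Share already above |
|---|---|---|---|---|
| 85 | 0.5 | 0.0735 | 0.0210 | 28.5% |
| 85 | 0.7 | 0.0735 | 0.0318 | 43.2% |
| 95 | 0.5 | 0.3264 | 0.1773 | 54.3% |
| 95 | 0.7 | 0.3264 | 0.2126 | 65.1% |

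The range is about 28% to 65%.

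**Possible effect of test mix (assumption, not from the documents).** Take fasting glucose with mean 90 and SD 10, 2-hour glucose with mean 115 and SD 30, one test per tested woman, and no treatment effect. Then P(fasting > 99.5) = 0.171 and P(2-hour > 199.5) = 0.0024. If 80% of tested women in one arm had the fasting test and 20% had the OGTT, the rate is 0.8 × 0.171 + 0.2 × 0.0024 = 13.7%. With the split reversed in another arm, it is 0.2 × 0.171 + 0.8 × 0.0024 = 3.6%. The 80/20 split is deliberately extreme. It shows that test choice alone can produce a difference, not that it will.

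**The case against.** The strongest reply is that the size is conjecture. The documents give no glucose distribution, event rate or test mix. The calculation of carry-over uses study-visit glucose in every woman, whereas the planned outcome uses routine tests in women judged at risk. Many women may have no test, and one above 99 mg/dL at visit 1 becomes a case only if a test is ordered and recorded, or if the study glucose counts, which the plan leaves unclear. This stands, and the figures are illustrative only.

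Randomization also balances raised glucose at entry in expectation. Including existing cases therefore mainly inflates the rate and dilutes a contrast, with only chance imbalance between arms. This stands too. It does not cover test ordering, which happens after allocation and is open to knowledge of the arm, although the documents do not show that ordering will differ.

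Several stronger readings are tempting but unsupported:

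- **That the outcome counts mostly raised or pre-existing fasting glucose.** Under wider assumptions (fasting mean 85-95, SD 8-12; 2-hour mean 110-125, SD 30-35), the fasting limb supplies 70% to over 99% of events if half the women have the fasting test, but 20% to 97% if only a tenth do. The share of events in women already above 99 mg/dL at baseline runs from 14% to 68%.
- **That the fasting cut-off sits at the trial's typical woman.** Glucose 100 mg/dL with insulin 1.4 × 405 / 100 = 5.67 gives the planned control HOMA-IR of 1.4, but so does 90 with 6.3 or 80 with 7.1. HOMA-IR fixes only the product.
- **That the two limbs stand for different diagnostic levels.** The documents contain no standard against which to show this.
- **That the diagnosis wording contradicts the definition.** It can be read as meeting the parent definition. It is ambiguous rather than contradictory.

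**Conclusion.** The concern holds in a limited form. As written, the plan can count glucose already raised at entry, or untreated diabetes, as newly developed, and it leaves ascertainment to whichever routine test was ordered. That follows from Sections 3.4 and 5 without any outside figure.

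How often it would happen cannot be derived from the documents. The 28% to 65% range holds only if study-visit fasting glucose is used and the assumed mean, SD and correlation apply. A reader might infer that the diabetes rate will be wrong in every arm. The documents do not support that certainty: the rate may be inflated, by an unknown amount. This is one of several secondary outcomes, so the point is worth correcting but does not threaten the primary comparison.

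**What to change.** 1. State the source of each limb, and reconcile both with the wording on women diagnosed with diabetes mellitus, so that one definition governs the outcome and its medication sub-item. This review does not say which cut-off is right.
2. Report the two limbs separately, and label the first as fasting glucose above 99 mg/dL.
3. Limit 'development' to women who did not meet the definition at visit 1 and have no known diabetes in the chart. Section 3 already provides for record review from the start of obstetric care. Visit 1, at 2-3 weeks, appears to follow randomization, and the plan does not say whether the diet starts before it. State the order, and show counts for all randomized women alongside.
4. Ascertain the fasting limb in all women from the study fasting glucose at visits 1 to 3. State that this is research classification, not the clinical diagnosis that Section 3.1 rules out. Report how many women in each arm had each routine test.

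The cost is revised outcome wording and one baseline flag, from data already being collected. The downside is a lower diabetes count and a slightly smaller at-risk set.

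### Worsening blood pressure has two event rules, one of which counts unchanged women; the diabetes outcome does not use the fasting glucose planned for every woman

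*Combined protocol and SAP*

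**What the plan says.** All of the text at issue is in the combined protocol and SAP.

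**Blood pressure.** In section 3.4, Secondary outcomes, the bullet defines worsening as a reading of 140/90 mm Hg or more, "or use of anti-hypertensive medication or increased dose of anti-hypertensive medication". Numbered item 3, in the same section, describes a comparison: "Blood pressure recorded at the time of enrollment to the blood pressure recorded at the 3 month postpartum study visit", and likewise at 6 months. On medication it says: "The addition of an anti-hypertensive medication or increased dose of an anti-hypertensive medication will be accessed by the research staff through chart review". It gives no threshold and no size of change.

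**Eligibility.** Section 5 does not list hypertension or antihypertensive treatment. It leaves other serious conditions to the investigator's discretion, and its examples do not include hypertension. For diabetes it excludes "Diabetes mellitus on medication; gestational diabetes requiring medication at the recruitment visit".

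**Diabetes.** The outcome rests on a "fasting plasma glucose test >99mg/dL or the 75-g, 2-hour OGTT > 199mg/dL", with a sub-bullet on medication: "Initiation (if newly diagnosed postpartum) or continuation/restarting (if had gestational diabetes and now diagnosed as diabetes mellitus) of insulin and/or oral medications". Item 2 names the source of the tests: "These tests are part of routine clinical care (when indicated) and will be accessed by the research staff through chart review". Sections 3 and 3.1 plan fasting glucose and HbA1c for all women at all three visits, but item 2 does not mention those values.

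**Analysis and masking.** Section 12 assigns ANOVA or a non-parametric equivalent to all outcomes and names chi-square only in its sentence on descriptive statistics. Section 2 calls the trial non-blinded. Section 3.4 closes with a masked review, stated for the primary outcomes only.

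**The concern.** An outcome called worsening should require change. The bullet does not: a woman on the same drug and dose since before randomization meets it at every follow-up visit. Item 3 does look for change, but does not say how much. Two analysts following the two texts could report different event counts from the same data. The choice between them is open in a non-blinded trial, and the stated masked review does not clearly reach this outcome.

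The starting point is also loose. Recruitment takes place during the postpartum hospital stay (section 3.1), while study vital signs are described only for visits 1 to 3, the first at 2-3 weeks. The enrolment reading therefore appears to be a chart value, and the plan does not say which one.

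For diabetes, tests ordered when clinically indicated classify only the women who had them, and no rule covers the rest. Because section 5 excludes diabetes mellitus only when it is treated, untreated diabetes already on record could also be counted as having developed postpartum.

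**Working it through.** **1. The two blood pressure rules, case by case.**

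| Woman, enrolment to follow-up | Bullet | Item 3 |
|---|---|---|
| Same treatment and dose, below 140/90, no rise | Event | Not an event |
| At or above 140/90 at both times, no rise, no drug change | Event | Not an event |
| Rises but stays below 140/90, no drug | Not an event | Possibly worse; no size of rise is stated |
| Untreated and below 140/90, later at or above it | Event | Worse |
| Drug added or dose raised | Event | Event |

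The rules agree in the last two rows and can disagree in the first three.

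**2. Size.** The plan gives no event rate and no power for this outcome, so there is no figure of its own to reproduce. The only input from the documents is the number per arm: 288 / 3 = 96 (section 12).

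Let p be the share of women whose condition is unchanged but who meet the bullet, and e the rate of new events in the rest.

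- Bullet count per arm: 96 × [p + (1 − p)e]
- Count requiring change: 96 × (1 − p)e
- Difference: 96 × p, whatever the value of e

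For p = 1% the difference is 96 × 0.01 = 0.96, about 1 event per arm. With the 321 / 3 = 107 randomized per arm it would be 1.07.

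The values of p and e below are assumptions, for illustration only:

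| p | e | Bullet | Change required | Difference |
|---|---|---|---|---|
| 5% | 5% | 9.4 | 4.6 | 4.8 |
| 10% | 5% | 13.9 | 4.3 | 9.6 |
| 30% | 10% | 35.5 | 6.7 | 28.8 |

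The fourth column is a count that requires change. It is not item 3 itself, which cannot be counted because it sets no size of rise.

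**3. Bias or noise.** The condition exists before randomization, so its expected share is p in every arm. If these women stay unchanged in all arms, they add p to each arm's rate and cancel from the expected difference: [p + (1 − p)c] − [p + (1 − p)t] = (1 − p)(c − t), where c and t are the new-event rates under control and diet. The difference is diluted and no arm is favoured. If diet did alter their status, the result could move either way, and the documents give nothing to settle it.

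**4. Diabetes sources.** Item 2 covers women tested in routine care. Sections 3 and 3.1 cover every woman who attends, with a fasting glucose that can be set against the protocol's own fasting criterion. Section 3.1 bars use of study data for clinical diagnosis; it does not bar classification for research.

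**5. Test for yes/no outcomes.** Take invented counts of 19, 10 and 10 events of 96. The expected count is 39 / 3 = 13 per arm and the overall rate is 39 / 288 = 0.1354. Chi-square = [(36 + 9 + 9) / 13] / (1 − 0.1354) = 4.80, p = 0.0905. Kruskal-Wallis = 4.80 × 287 / 288 = 4.79, p = 0.0913. ANOVA gives p = 0.0910.

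**The case against.** The strongest reply is that the two blood pressure texts belong together. The criteria sit under a title that says worsening, and item 3 is introduced as the way in which the listed outcomes will be reviewed. The threshold and drug criteria would then be judged against enrolment. That reading is plausible, but the text does not state it. It also leaves a conflict: unchanged drug use counts in the bullet and is absent from item 3.

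A reader might infer several stronger points that the documents do not support.

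- **A bias between arms or a known loss of power.** Pre-existing hypertension should be balanced in expectation, and no rates are given from which power could be calculated.
- **That the diabetes status of untested women cannot be known.** Fasting glucose and HbA1c are planned for all women at every visit. The gap is that item 2 does not use these values and gives no rule for women without a clinical test.
- **That testing will differ by arm.** This is possible in a non-blinded trial, but nothing shows it.
- **That ANOVA invalidates the yes/no comparisons.** The p-values above are nearly identical. What is missing is an effect estimate with its interval.

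**Conclusion.** The blood pressure point holds as an internal inconsistency. The bullet, followed as written, counts women who have not changed, and it can give a different total from item 3. The size is about 1 extra event per arm of 96 for each 1% of women with an unchanged condition. This rests on such women being enrolled, which section 5 permits, and the documents do not say how many there will be. The expected harm is noise and a label that does not match what is counted.

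The diabetes point holds in a limited form: the named source leaves women without a clinical test unclassified, while a suitable measurement is already planned for all attenders. The analysis point is a minor reporting matter.

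Only secondary outcomes are touched. The HOMA-IR outcome and the 288 and 321 sample sizes stand apart from this issue. The wording should still be settled before outcome data are reviewed.

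**What to change.** **Blood pressure (section 3.4).** Reconcile the bullet and item 3 into one event rule that requires change from the pre-randomization reading or medication status. Say what counts as change for women already at or above 140/90 or already on treatment. Name the chart reading that serves as the enrolment value. State the denominator: all women, or only those without the condition at enrolment.

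**Diabetes (section 3.4).** Keep the chart diagnoses. In addition, classify every attending woman from the study fasting glucose at visits 2 and 3 against the protocol's own fasting criterion, for research only, and report this as status at 3 and 6 months. Report chart-based diagnoses separately, with the number untested in each arm. Do not count diabetes mellitus recorded before randomization as having developed postpartum. This is an outcome rule: eligibility does not change, and women with gestational diabetes stay in, as the medication sub-bullet foresees.

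**Analysis (section 12, minor).** Report these yes/no outcomes with risk differences or ratios and confidence intervals.

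**Cost.** Wording in two sections, using data already planned. The drawbacks are fewer counted blood pressure events, and a glucose-based measure that shows status and not onset.

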### **3.1. Study visits/Follow-up**

#### **Screening recruitment and consenting**

##### Screening

Under the direction of the PI, trained research staff will be available to screen and consent subjects according to study protocol. Medical records of all potential subjects with a BMI  $\geq 30$  kg/m^2 (calculated by weight at the final prenatal visit prior to delivery) will be reviewed and those who satisfy inclusion and exclusion criteria will be approached at UTMB and a written informed consent will be obtained. A screening log will be used to track all subjects approached for the study.

The potential subjects that are recruited for the study will be contacted by the PI, co-investigators, or other trained research staff during their postpartum stay in the hospital. There will be no recruitment for the research study prior to birth. Research staff will review patients' electronic medical record. The health care provider of the

potential subjects will be notified that the patient may qualify for this research study. The health care provider will inquire if the patient would like to discuss the study with research personnel. If so, research staff will discuss the study with the patient and invite her to take part in the research study. Subjects will be recruited, enrolled and consented in a private room in order to respect the privacy of potential subjects.

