#### **4. Criteria for inclusion of subjects:**

- Maternal age  $\geq 18$  years and  $<50$  years
- Delivery at UTMB
- BMI  $\geq 30$  kilograms/meters at the final prenatal visit prior to delivery
- Singleton gestation
- Accessibility to the internet
- A basic understanding and comprehension of the English language to be assessed by study personnel at the time of recruitment of the study.

As part of the consenting process, an assessment of comprehension and understanding of the English language will be performed. The potential subject will be given a sample of the X-PERT printed document. The potential subject will provide written answers to three questions about the sample material.

Understanding and comprehension of the English language will be assessed by the research staff consenting the patient for the study. The potential subject will be required to answer all three questions correctly in order to be a potential candidate for the study.

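### Worsening blood pressure is defined in two conflicting ways, and weight and pressure are compared with no baseline covariate and no named source for the enrolment weight

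*Combined protocol and SAP*

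**What the plan says.** Section 3.4 (Secondary outcomes) describes each outcome twice, in a bullet list and then in a numbered list of how it will be reviewed.

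- **Blood pressure, bullet.** The event is a pressure at or above 140/90 mm Hg, or "use of anti-hypertensive medication or increased dose of anti-hypertensive medication". Neither the threshold nor the first half of the medication clause refers to the woman's status at enrolment.
- **Blood pressure, item 3.** The comparison is "Blood pressure recorded at the time of enrollment to the blood pressure recorded at the 3 month postpartum study visit", and likewise at 6 months. Medication matters when it is added or its dose is raised.
- **Weight, item 1.** The outcome is "Change from baseline body weight at enrollment of study", set against the 3- and 6-month weights.

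On timing, section 3.1 (Screening) says that potential subjects "will be contacted by the PI, co-investigators, or other trained research staff during their postpartum stay in the hospital", and it rules out recruitment before birth. The three study visits are where "vital signs, including blood pressure, waist circumference, height and weight, will also be recorded"; the first is 2-3 weeks after delivery. Section 3 also lists weight and pressure among the data taken by chart review. The only weight before visit 1 that the text names is the one "at the final prenatal visit prior to delivery", used for the eligibility BMI.

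Section 5 does not list hypertension as an exclusion. Section 12 compares primary and secondary outcomes by ANOVA or a rank-based counterpart and names no baseline covariate. It mentions multivariable analysis only for describing the population and looking for confounders.

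**The concern.** The two blood-pressure descriptions give different event counts from the same data. The bullet, taken alone, records whether a woman is hypertensive or treated at follow-up. Item 3 records whether she has got worse. Only the second matches the outcome's name. With hypertensive women eligible, the bullet mixes existing with new disease, and an analyst could choose between the definitions after seeing the data.

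The weight outcome rests on an enrolment value with no stated source or time. Enrolment is in hospital, no study visit falls there, and the one early weight named was taken before delivery. If that weight is used, the change reported within each group may contain the weight lost at delivery and could be misread as response to diet.

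For both outcomes, a comparison that leaves out an available pre-randomization value gives up precision that costs almost nothing to recover.

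**Working it through.** **The plan's own figure.** Section 12 gives 96 per group from HOMA-IR means 1.4, 1.05 and 1.05 and within-group variance 0.8. The grand mean is 3.5/3 = 1.1667. The squared deviations sum to 0.0544 + 0.0136 + 0.0136 = 0.0817, so the noncentrality is 96 × 0.0817/0.8 = 9.8, and the F test has power 80.3%. With 10% loss, 96/0.9 rounds up to 107 per group, or 321. The figure reproduces. It concerns HOMA-IR only; the plan gives no SD, effect or power for weight or blood pressure.

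**The two blood-pressure definitions side by side.**

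| Woman | Bullet | Item 3 |
|---|---|---|
| At or above 140/90 at enrolment, untreated; same at follow-up | counts | does not count |
| On medication at enrolment, same drug and dose, pressure unchanged and below 140/90 | counts | does not count |
| Pressure higher than at enrolment but below 140/90, untreated | does not count | unclear: no size of rise is given |
| Newly at or above 140/90, or medication added | counts | counts |

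The documents give no prevalence of hypertension at enrolment. Each percentage point of women in the first two rows adds about 107 × 0.01 = 1 event per group under the bullet and none under item 3. To the extent that diet does not alter these women's status, the added events are common to all groups in expectation and pull a risk ratio towards 1.

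**Baseline adjustment for pressure.** Assume equal variance σ² at enrolment and follow-up, with correlation ρ.

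- Change score: 2σ²(1 − ρ)
- Follow-up value alone: σ²
- ANCOVA: σ²(1 − ρ²)

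Change score over ANCOVA is 2/(1 + ρ): 2/1.3 = 1.54 at ρ = 0.3 and 2/1.6 = 1.25 at ρ = 0.6. Follow-up alone over ANCOVA is 1/(1 − ρ²): 1/0.91 = 1.10 and 1/0.64 = 1.56. The correlations are assumptions. ANCOVA has the smaller variance in both comparisons.

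**Baseline adjustment for weight.** Weight tracks closely over time. At assumed ρ = 0.90, 2/1.90 = 1.05; at 0.95, 2/1.95 = 1.03. The gain over a change score is a few per cent.

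**Effect of the weight anchor.** A simulation with 96 per group assumed a delivery-related loss with mean 6 kg and SD 2.5 kg in both groups, no other mean change in controls, and a true difference of −2.0 kg. The mean change in controls was about −6.0 kg, while the between-group difference averaged −2.02 kg. So the within-group figure moves and the contrast does not.

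**The case against.** **The weight baseline may be sound.** The plan does not say that the prenatal weight is the baseline; it uses that weight only for eligibility. A weight taken after birth would already exclude infant and placenta. One could also read visit 1 as the baseline, since three visits record weight and the outcome names the other two. This stands as far as it goes: the text does not settle the source. A reader might infer that reported change certainly includes delivery loss. The documents support only that it may.

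**Loss of precision in weight.** A reader might also infer that an in-hospital anchor adds avoidable noise. With assumed SDs of 2-4 kg for early loss and 5-6 kg for later change, independent of each other, variance relative to change from visit 1 would rise from (4 + 36)/36 = 1.11 to (16 + 25)/25 = 1.64 times. The documents do not support this. They give none of these SDs and no ground for independence. Under that same model, the ANCOVA slope on enrolment weight is 1, so its residual variance equals that of the change score (40 and 41) and adjustment recovers nothing. A visit-1 baseline would remove the noise, but visit 1 follows randomization and may follow the start of the diet, for which no date is given. It could therefore absorb early treatment effect.

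**Blood pressure.** The bullet's dose clause is already relative to earlier treatment, item 3 contains most of what is needed, and the investigator may exclude other serious conditions at discretion. All true. Yet the bare threshold and any use of medication still conflict with item 3, and discretion is not an exclusion of hypertension. The plan names no continuous pressure change score, so the 1.25-1.54 ratio is conditional on that analysis.

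**Conclusion.** The concern holds in limited form and for secondary outcomes only.

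- **Blood pressure.** The two definitions conflict on the face of the text, with no assumption needed. The number of events affected cannot be sized from the documents.
- **Adjustment.** No baseline covariate is prespecified. For pressure analysed as change, the variance is 1.25-1.54 times that of ANCOVA, given equal variances and a correlation of 0.3-0.6. For weight the gain is probably small.
- **Weight baseline.** Its source is unstated. Within-group change may include delivery-related loss if the prenatal weight is used.

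None of this biases the comparison between randomized groups, and the primary outcome and the sample size of 321 stand.

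**What to change.** 1. Reconcile the bullet and item 3 into one definition of worsening blood pressure, judged against each woman's own enrolment pressure and medication. The investigators should state what size of change in pressure counts. The cost is fewer events. If hypertension at follow-up is also of interest, report it separately under that name.
2. In section 12, analyse 3- and 6-month weight, systolic pressure and diastolic pressure by ANCOVA, with one named pre-randomization chart value of the same measure as covariate. With that covariate in the model, using follow-up weight or weight change as the response gives the same group difference.
3. State the source and timing of the enrolment weight and pressure, and use the same source for every woman.
4. Report weight change from the measured visit-1 weight descriptively, noting that visit 1 falls after randomization.

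The cost is mainly wording, provided that the charts hold the enrolment values. The eligibility weight must exist for every woman; the presence of a chart pressure before randomization should be confirmed.
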